9.2 Overview of Efficacy Evaluations

* Patients who have no evidence of disease on CT at baseline can omit follow-up scans unless palpable disease arises or there is clinical suspicion of disease progression.

Always consult Tables in Section 6 and 9 for details of all investigations required.

9.3 Evaluation After Protocol Treatment

All patients will be seen 4 weeks after the end of the last cycle (4 Week Post Treatment Report).

Patients whose treatment is permanently discontinued due to an adverse event or non-hepatic clinically significant laboratory value, should be followed as clinically indicated until resolved to \leq grade 2. See Section 8.4.3 for more detailed guidance on patients who discontinue study treatment due to hepatic toxicity.

Follow-up beyond the 4 week treatment report is not required for patients who go off protocol treatment with progressive disease, except to document ongoing toxicities (until resolved to \leq grade 2), late toxicities (including second malignancies) and death if within 30 days of last dose.

For patients who go off protocol treatment with objective CR, PR or SD ongoing, follow up including response assessment will be required every three months until relapse/progression (Follow-Up Report). If the patient starts new anticancer therapy, contact the study coordinator to discuss whether further follow-up is required.

For patients who go off protocol therapy with suspected PR or CR, an 8 week confirmatory response assessment including CT scanning will be required as per Sections 9.1 and 10.4, if not already performed.

A Death Report is only required if death occurs within 30 days of last dose or if patient dies before progression/relapse; due within 2 weeks of knowledge of death (see Appendix IV –Documentation for Study).

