11.1 Definition of a Reportable Serious Adverse Event

- All serious adverse events, regardless of whether they are unexpected or related to protocol treatment, occurring during the treatment period and within 30 days after the last protocol treatment administration, must be reported in an expedited manner. Any late serious adverse event occurring after this 30-day period which is unexpected and related to protocol treatment must also be reported in an expedited manner (see Section 11.2 for reporting instructions).
- A serious adverse event (SAE) is any adverse event that at any dose:
 - results in death
 - is life-threatening
 - requires inpatient hospitalization or prolongation of existing hospitalization (excluding hospital admissions for study drug administration, transfusional support, scheduled elective surgery and admissions for palliative or terminal care)
 - results in persistent or significant disability or incapacity
 - is a congenital anomaly/birth defect

Medical and scientific judgement should be exercised in deciding whether expedited reporting is appropriate in other situations such as important medical events that may not be immediately life-threatening or result in death or hospitalization but may jeopardize the patient or may require intervention to prevent one of the events listed above.

Note: Adverse events which are unequivocally only related to the underlying malignancy or disease progression are NOT reportable Serious Adverse Events. These include such adverse events as admission for pain control, palliative care or paracentesis of malignant effusions.

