12.0 PROTOCOL TREATMENT DISCONTINUATION AND THERAPY AFTER STOPPING

12.1 Criteria for Discontinuing Protocol Treatment

Patients may stop protocol treatment in the following instances:

- Intercurrent illness which would, in the judgement of the investigator, affect assessments of clinical status to a significant degree, and require discontinuation of protocol therapy.
- Unacceptable toxicity as defined in Section 8.0.
- Progression or disease recurrence as defined in Section 10.0.
- Request by the patient.
- Completion of therapy as outlined in Section 8.0. Efforts should be made to maintain the investigations schedule and continue follow-up, even if patients discontinue protocol treatment prematurely and/or no longer attend the participating institution.

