12.2 Duration of Protocol Treatment

(see Section 10.0 for response definition)

- For patients who achieve a complete or partial response, therapy will continue until objective disease progression or unacceptable toxicity, whichever occurs first.
- For stable patients, therapy will continue for a maximum of 6 cycles (24 weeks). Patients who have no evidence of tumour shrinkage at this point should go off therapy and receive other treatment at the investigator's discretion.
- Patients who progress (treatment failure) will go off study at the time progression is documented clinically and/or radiographically.

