14.5 Prospective Validation of Survival Scale

We have previously designed and validated a scale which can predict 90 day mortality among patients with hematological malignancies enrolled in Phase I and II clinical trials [*Jamal 2012*]. This scale uses 5 easy to measure, objective clinical variables, including albumin, LDH, diagnosis (AML vs non AML), platelet count and alkaline phosphatase. Each is attributed one point. A patient having 3 or more points has up to a 40% chance of mortality within 3 months of treatment on a clinical trial. The initial validation did not include patients with CLL. We therefore intend to validate this scale in CLL in the context of this trial.

The scale will be applied to each individual patient and mortality risk calculated. A Kaplan Meier survival curve will be generated and hazard ratio for death estimated comparing low and high risk patients within this study, in order to determine the ability of the scale to distinguish mortality risk between these two groups.

AMEND #3: 2016-AUG-24

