RELAPSE/PROGRESSION REPORT	To be completed at the time of disease relapse or progression. Due within 2 weeks after contact with patient.	Relevant radiology reports.

continued on next page ...

Form	To be Completed/Submitted Electronically:	Supporting Documentation to be sent using Supporting Document Upload Tool
DEATH REPORT	Required only on patients who die during protocol therapy, within 30 days after last dose, or within the protocol defined follow-up period for patients with response or stable disease ongoing.* Due within 2 weeks of knowledge of death.	Autopsy report, if done.
SERIOUS ADVERSE EVENT REPORT FORM	All reportable serious adverse events must be reported as described in Section 11.0. All reportable serious adverse events must be reported as described in Section 11.0. Preliminary CCTG Serious Adverse Event Report due within 24 hours. Updated CCTG Serious Adverse Event Report due within 7 days .	
* NB It is the investigator's responsibility to investigate and report the date/cause of death of any patient who dies during this period. Any death that occurs during this period and that is thought to be treatment related must also be reported as a Serious Adverse Event as described in Section 11.		

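### Section 14.5 plans a survival curve and death hazard ratio with no time limit, but Section 9.3 does not require most deaths after progression to be reported once 30 days have passed since the last dose

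*Protocol*

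**What the plan says.** Section 14.5 describes a five-item scale for 90-day mortality in haematological malignancy, not yet validated in CLL. Its only figure is: "A patient having 3 or more points has up to a 40% chance of mortality within 3 months". The planned analysis is: "A Kaplan Meier survival curve will be generated and hazard ratio for death estimated comparing low and high risk patients within this study". No horizon, number of deaths or power is given.

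Section 9.3 sets what sites must send: "A Death Report is only required if death occurs within 30 days of last dose or if patient dies before progression/relapse". For patients who stop with progressive disease it adds: "Follow-up beyond the 4 week treatment report is not required for patients who go off protocol treatment with progressive disease", with exceptions for toxicities and for death within 30 days of last dose. Appendix IV gives the same rule for the Death Report: "Required only on patients who die during protocol therapy, within 30 days after last dose, or within the protocol defined follow-up period", the last part being for patients whose response or stable disease is ongoing. Section 9.3 also refers sites to the study coordinator on whether follow-up continues once new anticancer therapy starts.

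Other relevant places:
- Section 12.1: "Efforts should be made to maintain the investigations schedule and continue follow-up, even if patients discontinue protocol treatment prematurely".
- Section 12.2: progressing patients "will go off study at the time progression is documented", and progression may be clinical or radiographic.
- Section 11.1: "Any late serious adverse event occurring after this 30-day period which is unexpected and related to protocol treatment must also be reported".
- Section 14.2: six months of follow-up after the last enrolment, without mention of vital status.
- SAP: a Kaplan-Meier plot for PFS is the only survival-type figure named. Tables 1 to 12 are not shown.

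**The concern.** Kaplan-Meier and hazard-ratio estimates assume that patients whose follow-up ends have the same later risk of death as those still followed. Here required capture ends because the disease has progressed (or, later, 30 days after the last dose), and progression probably changes the risk of death. The deaths that need not be reported are those after progression.

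The curve and hazard ratio meant to validate the scale could therefore rest on an incomplete and selective count of deaths in at most 29 patients. Sites may volunteer later deaths, but nothing requires it, and voluntary reporting could be uneven.

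**Working it through.** Section 14.5 contains no calculation to reproduce; the sample size in Section 14.2 concerns response only.

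**1. Where required capture ends.** From Section 9.3: capture end = the later of (documented progression, last dose + 30 days). Gap to day 90 = 90 − capture end, if positive.

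| Last dose (day) | Progression (day) | Capture end | Gap to day 90 | Gap to day 180 |
|---|---|---|---|---|
| 28 | 28 | 58 | 32 | 122 |
| 42 | 42 | 72 | 18 | 108 |
| 56 (week-8 CT) | 56 | 86 | 4 | 94 |
| 60 | 60 | 90 | 0 | 90 |
| 20 | 80 | 80 | 10 | 100 |
| 150 | 150 | 180 | 0 | 0 |

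The late-SAE exception would recover a few deaths. The new-therapy clause could end capture sooner.

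**2. Assumptions for size.** The documents give no medians. A grid of 90 cells used exponential medians: progression 45, 60, 90, 180 or 365 days; survival after progression 30, 45, 60, 120, 240 or 365 days; death before progression none, 180 or 90 days. CT falls on days 56, 112 and 168, then every 84 days (Section 9.1). Error = Kaplan-Meier mortality minus true mortality, in percentage points.

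**3. One day-90 cell by hand.** Progression median 45, later survival median 30 from detection, no death before progression, dosing until the CT that finds progression.
- Progressed by the day-56 CT: 1 − 2^(−56/45) = 0.578.
- True mortality at day 90: 0.578 × (1 − 2^(−34/30)) = 0.578 × 0.544 = 31.4%.
- Capture stops on day 86, so Kaplan-Meier gives 0.578 × (1 − 2^(−30/30)) = 28.9%.
- Error: −2.6 points, the low end of the grid in step 5.

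**4. One day-180 cell by hand.** Progression 45, later survival 60, otherwise the same. Let p = 0.578 and q = 1 − p = 0.422.
- True mortality: p(1 − 2^(−124/60)) + qp(1 − 2^(−68/60)) + q²p(1 − 2^(−12/60)) = 0.440 + 0.133 + 0.013 = 58.6%.
- Kaplan-Meier: 1 − [1 − p(1 − 2^(−30/60))]² × [1 − p(1 − 2^(−12/60))] = 1 − 0.831² × 0.925 = 36.2%.
- Error: about −22.5 points.

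The opposite sign also occurs. With progression 45, later survival 365 and death before progression 90, simulation gives 56.6% true and 67.9% Kaplan-Meier at day 180, an error of +11.3.

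**5. Ranges over the grid (simulation).**

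| Case | Day 90 | Day 180 |
|---|---|---|
| CT, dosing to progression, hazard changes at detection | −2.6 to +0.8 | about −23 to +11 |
| Same, hazard changes at progression itself | about −0.9 to +0.6 | about −10 to +8 |
| CT, dosing stops early (assumed median 60 or 120 days) | about −8 to +2 | about −38 to +14 |
| Progression documented as it occurs, dosing to progression | about −9 to +5 | about −22 to +15 |

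Unreported deaths by day 90 per 29 patients: 0.01 to 0.75 in the first case, and up to nearly 4 with early stopping.

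**6. Hazard ratio.** With assumed hazards, equal risk groups and CT detection, the 24-month hazard ratio moved from 1.44 to 2.73 in one scenario and from 13.9 to 12.6 in another. It too can move either way.

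**The case against.** The scale targets 90 days, and that horizon is nearly covered when dosing continues to a scheduled CT. With 29 patients and 20% mortality the standard error is √(0.2 × 0.8 / 29) = 7.4 points, well above the 2.6-point error in that case. This stands, and it is one reason the point is minor. It does not cover patients who stop early under the toxicity rules of Section 8.4, or who progress clinically before week 8.

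The assumed medians include pessimistic cells: with scheduled CT the implied 90-day mortality in all patients reaches 62%, although entry requires a life expectancy of at least 12 weeks and the 40% figure is a ceiling for high-risk patients only. The day-180 range roughly halves if the hazard changes at progression instead of at detection. Equal risk groups have no support in the documents, since one scale item is an AML diagnosis. All of this stands, so the ranges show what could happen and are not forecasts.

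Section 9.3 also has every patient seen 4 weeks after the end of the last cycle. If a patient stopping on day 42 is counted to the end of a 28-day cycle, the visit falls on day 84 and the gap is 6 days instead of 18. Appendix I counts from coming off therapy, so this is unclear. It helps only mid-cycle stops; the gaps for days 28 and 56 do not change.

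A reader might infer that the 90-day validation is invalid, or that mortality will be understated. The documents support neither: the day-90 effect depends on when dosing stops and how progression is found, and the bias has either sign. It is zero if progression does not change the death hazard.

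**Conclusion.** The mismatch is in the text. An open-ended survival analysis is planned, and the deaths it needs after progression are mostly not required. Best efforts (12.1), going off study (12.2), late related SAEs (11.1), the six-month follow-up (14.2) and the visible SAP do not close the gap.

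Severity is minor. At day 90 the effect is small if dosing continues to progression at a scheduled CT, and can reach several points otherwise. Beyond day 90 it can be large, with direction and size not determinable from the documents. Every size rests on assumed medians, on the time at which the hazard changes, and on sites sending no more than is required.

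A reader might extend this to the main results. That does not follow: response rate, response duration and PFS do not need deaths after progression. Only objective 1.2.4 is affected.

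**What to change.** In Section 9.3 and Appendix IV, require vital status (date of death or date last known alive) at day 90 after registration for every patient, whatever the progression status or later therapy.

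In Section 14.5, report observed 90-day mortality by risk group, and limit the Kaplan-Meier curve and hazard ratio to day 90. Extend them further only if vital status at the final data cut is also collected for every patient.

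Cost: one chart or phone entry per patient for at most 29 patients (two if the final cut is added), amendment wording, and any consent wording needed for the later contact. No new visit or procedure is involved.

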10.0 CRITERIA FOR MEASUREMENT OF STUDY ENDPOINTS

10.1 Definitions

10.1.1 Evaluable for Response

All patients who have received at least one cycle of therapy and have their disease re-evaluated will be considered evaluable for response (exceptions will be those who exhibit objective disease progression prior to the end of cycle 1 who will also be considered evaluable). Patients on therapy for at least this period and who meet the other listed criteria will have their response classified according to the definitions set out below, as recommended by Revised International Workshop on Chronic Lymphocytic Leukemia 2008 [*Hallek 2008*] and incorporating updated recommendations for refinement of clinical trial endpoints when using novel targeted agents [*Cheson 2012*].

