10.4 Response

All patients will have their BEST RESPONSE from the start of study treatment until the end of treatment classified as outlined below. In patients with limited disease at study entry, response will be assessed using only parameters that were abnormal at baseline.

Complete Response (CR): CR requires all of the following criteria, maintained for a period of at least 8 weeks.

- Peripheral blood lymphocytes (evaluated by blood and differential count) $< 4 \times 10^9/L$;
- Absence of significant lymphadenopathy > 1.5 cm in diameter on physical examination and CT scan

- No hepatomegaly or splenomegaly by CT scan
- Absence of constitutional symptoms attributable to disease
- Normal blood counts above the following values:
 - Neutrophils more than $1.5 \times 10^9/L$ without need for exogenous growth factors
 - Platelets more than $100 \times 10^9/L$ without need for exogenous growth factors
 - Hemoglobin more than 110 g/L without red blood cell transfusion or need for exogenous erythropoietin.
- A marrow aspirate and biopsy should be performed to demonstrate that a CR has been achieved at the time other criteria for CR are met.
 - To define a CR, the marrow sample must be at least normocellular for age, with < 30% of nucleated cells being lymphocytes. Lymphoid nodules should be absent. If lymphoid nodules are found, they will often reflect residual disease. These nodules should be recorded as "nodular PR". Immunohistochemistry should be performed to define whether these nodules are composed primarily of T cells or lymphocytes other than CLL cells.
 - If the marrow is hypocellular, a repeat determination should be performed after 4 weeks, or when peripheral blood counts have recovered. However, this time interval should not exceed 6 months after the last treatment. A marrow biopsy should be compared with that of pretreatment marrow.
 - Optional: The quality of the CR may be assessed for minimal residual disease by flow cytometry or by immunohistochemistry (IHC).
- Patients who fulfill all the criteria for a CR (including the marrow examinations described above) but who have a persistent anemia or thrombocytopenia or neutropenia apparently unrelated to CLL but related to drug toxicity will be considered as CR with incomplete marrow recovery (CRi). A repeat bone marrow should ideally be done in these patients when counts recover fully. If the bone marrow at this time reveals no CLL, these patients will be considered as having CR at that time.

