 - The progression of any cytopenia (unrelated to autoimmune cytopenia), as documented by a decrease of Hb levels by more than 20 g/L (2 g/dL) or to less than 100 g/L, or by a decrease of platelet counts by more than 50% or to less than $100 \times 10^9/L$, which occurs at least 3 months after treatment, defines disease progression, if the marrow biopsy demonstrates an infiltrate of clonal CLL cells.

Note:

B cell receptor targeted drugs can mobilize CLL cells from tissues into the peripheral blood, interfering with their homing. This characteristic pharmacologic action can be prominent early in therapy, but can also persist over time. This occurrence should not be confused with PD unless the treated patient develops other CLL-related signs or symptoms of PD. In the absence of other objective evidence of PD, **lymphocytosis alone should not be considered an indicator of PD** [Cheson 2012].

Stable Disease (SD): Patients who have not achieved a CR or a PR, and who have not exhibited progressive disease, will be considered to have stable disease (which is equivalent to a nonresponse).

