14.2 Sample Size and Duration of Study

PI3K Inhibitor Naïve Cohort

The null hypothesis at which buparlisib will be considered of no value in this disease is an overall response rate of $\leq 5\%$. The alternative hypothesis at which the drug will be considered worthy of further study is $\geq 30\%$. Enrolment of 12 evaluable patients is required to test this hypothesis with a one-sided α of 0.1 and 80% power.

According to the Simon 2 stage design, 5 patients will be enrolled in the first stage. If at least one PR or CR is observed, then a total of 12 patients will be enrolled. When 2 or more patients among 12 evaluable patients achieve CR or PR, the null hypothesis will be rejected.

Exploratory Cohort

Outcomes of individuals previously treated with alternative PI3 kinase inhibitors will be presented descriptively. It is anticipated these numbers will be small, in which case any observed CR or PR will be of interest and considered worthy of further study. If for example 8 patients are enrolled, this would enable detection of a 5% versus 20% overall response rate with 53% power at a one sided α of 0.1. A maximum of 17 individuals will be enrolled on this exploratory cohort.

Overall

Accrual of up to 29 patients overall is anticipated to take place over 24 months. Follow-up of 6 months will be required after the last patient is enrolled. Thus, total duration of study is expected to be 30 months.

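### The response denominator in 10.1.1 leaves out treated patients who stop in cycle 1 without progression, so the evaluable-only rate modestly overstates the all-treated rate and should not be reported alone

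*Protocol*

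**What the plan says.** Section 10.1.1 of the protocol defines the response population: "All patients who have received at least one cycle of therapy and have their disease re-evaluated will be considered evaluable for response". It restores one group, patients with objective progression before cycle 1 is over. It then adds: "Patients on therapy for at least this period and who meet the other listed criteria will have their response classified according to the definitions".

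Section 10.4 opens more broadly: "All patients will have their BEST RESPONSE from the start of study treatment until the end of treatment classified as outlined below". Its stable-disease definition says that patients with neither CR nor PR and "who have not exhibited progressive disease, will be considered to have stable disease (which is equivalent to a nonresponse". Both CR and PR must hold for at least 8 weeks.

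Section 14.2, for the PI3K inhibitor naïve cohort, tests 5% against 30% at one-sided alpha 0.1 with 80% power. It says "Enrolment of 12 evaluable patients is required to test this hypothesis", then "5 patients will be enrolled in the first stage". It goes on to speak of 12 enrolled in total after a first-stage response, and ends: "When 2 or more patients among 12 evaluable patients achieve CR or PR, the null hypothesis will be rejected".

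The SAP text names no denominator for the response rate. It refers Tables 1 to 12 to a meeting book that is not among the documents.

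**The concern.** Whether a patient counts for response depends on something that happens after treatment starts: completing a cycle and being re-evaluated. Early progressors are brought back in, but early stops for toxicity, withdrawal or death without documented progression are not. For a question about what the drug achieves in patients who are given it, those are failures of treatment. Leaving them out removes non-responders from the denominator and almost nothing from the numerator, so the reported rate is pushed up.

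Such exits are foreseeable here. Section 8.4 makes several toxicities grounds for permanent discontinuation, and 8.1.1 plans a safety review after the first 3 patients.

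The second, smaller issue is the counting basis in 14.2. The first look is worded in enrolled patients and the final rule in evaluable patients. If a site or the central office took the first word literally, the interim decision could rest on fewer than 5 evaluable patients.

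**Working it through.** **Inputs.** From 14.2: p0 = 0.05, p1 = 0.30, stage 1 of 5 patients, continue with at least 1 response, total 12, reject with at least 2 responses. From 10.4: a response lasts at least 8 weeks. From 8.1.1: a cycle is 28 days. Assumed: q, the share of treated patients who are non-evaluable, at 5, 10 and 20%.

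**1. The plan's own design.** With n1 evaluable patients at the first look and n at the end, the chance of rejecting the null is

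R(p, n1, n) = 1 - (1-p)^n1 - n1·p·(1-p)^(n-1).

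- Alpha: R(0.05, 5, 12) = 1 - 0.7738 - 0.25 × 0.5688 = 0.084.
- Power: R(0.30, 5, 12) = 1 - 0.1681 - 1.5 × 0.01977 = 0.802.

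The stated design is correct for 5 and then 12 evaluable patients. The margin over 80% power is 0.2 points.

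**2. Direction and size of the bias.** A patient who leaves within a 28-day cycle has not been on treatment long enough to show an 8-week response. Section 9.3 allows a suspected response to be confirmed after treatment stops, so a confirmed response in this group is unlikely rather than impossible. Taking all of them as non-responders, with X responders among N treated:

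(evaluable rate)/(all-treated rate) = [X/(N(1-q))] / [X/N] = 1/(1-q).

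| Assumed q | Ratio |
|---|---|
| 5% | 1.05 |
| 10% | 1.11 |
| 20% | 1.25 |

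**3. At the cut-off.** Two responders among 12 evaluable is 16.7% (exact 95% CI 2.1 to 48.4%). If 2 further treated patients were non-evaluable, the all-treated rate is 2/14 = 14.3% (1.8 to 42.8%). The shift is 2.4 points, against intervals more than 40 points wide.

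**4. Counting basis at stage 1.** Suppose the first look is taken at 5 enrolled patients, one is non-evaluable, and accrual still runs to 12 evaluable.

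- Power: R(0.30, 4, 12) = 1 - 0.2401 - 1.2 × 0.01977 = 0.736.
- Chance of stopping at stage 1 when the true rate is 30%: 0.7^4 = 24.0%, instead of 0.7^5 = 16.8%.
- Alpha: R(0.05, 4, 12) = 0.072, still below 0.10.

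If all 5 are evaluable, nothing changes.

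**The case against.** A response-evaluable population fixed in advance is a legitimate choice, and 14.2 uses it. The bias is small beside the sampling error, and no value of q comes from the documents. Sections 10.1.1 and 10.4 can also be reconciled by taking the second sentence of 10.1.1 to limit 10.4 to evaluable patients. All of that stands. It limits the size of the point but does not remove it, because the rule as written still discards early toxic stops.

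Four stronger readings are tempting and are not supported.

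- **That power falls below 80% as the plan stands.** Section 14.2 calls the same final 12 both enrolled and evaluable, so enrolled is most naturally loose wording and stage 1 most naturally means 5 evaluable. The loss in step 4 needs both a literal reading and a non-evaluable patient in stage 1.
- **That 29 leaves no room for non-evaluable patients.** It is true that 12 + 17 = 29. But 29 is an anticipated upper figure, and for the other cohort the text says "A maximum of 17 individuals will be enrolled on this exploratory cohort", while expecting small numbers and using 8 as its example. With 8 there, 29 - 8 = 21 places remain for the naïve cohort.
- **That patients given high-dose steroids leave the denominator.** Sections 8.4.6 and 8.4.7 say only that they may become inevaluable for response assessment. Neither section removes them from the 10.1.1 population, and such a patient may already have responded.
- **That the SAP has no all-treated rate.** Tables 1 to 12 cannot be seen, so this cannot be judged.

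**Conclusion.** The point holds in a limited form. By the wording of 10.1.1, the evaluable-only response rate overstates the all-treated rate by a factor of about 1.05 to 1.25 for q between 5 and 20%. This rests on two assumptions: the range of q, and that cycle 1 leavers are essentially never confirmed responders. The second is well supported by the 8-week requirement. At the cut-off the effect is a few percentage points and would not by itself change how the trial is read, but a reader cannot see it unless both rates are given.

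The sample-size calculation in 14.2 is correct. The mixed use of enrolled and evaluable is a wording fault. It has a consequence (power 73.6% instead of 80.2%) only if stage 1 is run on 5 enrolled patients and one of them proves non-evaluable.

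**What to change.** 1. In 10.1.1, 10.4 and the SAP, keep the evaluable rate and report beside it the response rate, with exact confidence interval, in all eligible PI3K-naïve patients who received at least one dose. Count anyone without a confirmed CR or PR as a non-responder. List each non-evaluable patient with the reason, and say in 10.4 which set of patients its opening sentence covers.
2. In 14.2, write 5 evaluable patients for stage 1 and state that accrual continues until 12 are evaluable.

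The two changes belong together. Continuing to 12 evaluable replaces early toxic stops. If the 5% null were meant for all treated patients, which the documents do not say, R(0.05/(1-q), 5, 12) would pass 0.10 at q = 9.8%. The all-treated rate lets a reader see this.

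**Cost.** Wording only; the design, cut-offs, alpha and power stay as they are. Appendix IV already requires follow-up of all eligible and ineligible patients from registration. Reaching 12 evaluable takes 12/(1-q) = 12.6, 13.3 or 15.0 enrolled on average at q = 5, 10 or 20%, which a target of 12 evaluable already implies. The downside is a slightly lower rate printed beside the primary one.
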